## **STATISTICAL ANALYSIS PLAN**

### **8.3. Safety Analysis**

Safety analysis will be performed based on safety population.

Proportion (Count and percentage (%)) of subjects with the below will be presented:

- at least one TEAE,
- at least one serious TEAE,
- at least one severe TEAE,
- at least one TEAE suspected to be related to the investigational device,
- at least one adverse device effect (ADE),
- at least one serious adverse device effect (SADE),
- at least one unanticipated serious adverse device effect (USADE),
- and any deaths.

Proportion (Count and percentage (%)) of AEs/SAEs Incidence.

Proportion (Count and percentage (%)) of AEs/SAEs type.

Proportion (Count and percentage (%)) of AEs/SAEs characteristics including severity, relationship to procedure, relationship to device, action taken and outcome.

AEs with a related, probable, or possible relationship, or for which the relationship is missing, will be considered related.

TEAEs and serious TEAEs will be summarized at the subject level by MedDRA system organ class (SOC) and preferred term (PT) using frequencies and percentages.

TEAEs will also be summarized at the event level by SOC, PT, and severity and by SOC, PT, and relationship to the investigational device.

## **STATISTICAL ANALYSIS PLAN**

### **9. DERIVED DATA**

Adverse event duration will be calculated as (Onset date – Resolution date) + 1. For partial dates, if day is missing but month is available, the 15th of the month will be used as the date. If both month and day are missing, then January 15th of the year will be used. PillSense capsule passage will be calculated (Date of passage - Date of procedure)

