### **4. STUDY DESIGN**

This is a prospective, non-randomized, open-label clinical investigation to evaluate feasibility, effectiveness and safety of the PillSense System, the transit of the PillSense Capsule through the GI tract, patient tolerability of the PillSense Capsule, and blood detection. Observation will take place for each Patient up to a maximum 21 days.

[figure not shown]

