### 5.4. Safety Parameters

Safety will be assessed based on adverse events.

Summaries of adverse events (AEs) will be limited to treatment-emergent adverse events (TEAEs), which are those adverse events that begin or worsen after initiation of “treatment” with the investigational device (i.e., administration of the PillSense Capsule).

For AEs with a missing start date, the AE will be considered treatment-emergent unless there is additional information indicating that the AE started prior to study treatment.

The numbers and percentages of subjects with the below will be presented:

- at least one TEAE,
- at least one serious TEAE,
- at least one severe TEAE,
- at least one TEAE suspected to be related to the investigational device,
- at least one adverse device effect (ADE),
- at least one serious adverse device effect (SADE),
- at least one unanticipated serious adverse device effect (USADE), and any deaths.

AEs with a related, probable, or possible relationship, or for which the relationship is missing, will be considered related.

TEAEs and serious TEAEs will be summarized at the subject level by MedDRA system organ class (SOC) and preferred term (PT) using frequencies and percentages. TEAEs will also be summarized at the event level by SOC, PT, and severity and by SOC, PT, and relationship to the investigational device.

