## **STATISTICAL ANALYSIS PLAN**

outlier. If data points are identified as outliers sensitivity analysis may be performed to examine the impact of including or excluding the outliers. Any substantive differences in these analyses will be reported. It is assumed that all missing data will be random.

In mITT population, subjects with missing data will not be counted in the percentage. Number of missing values will be reported.

In Safety population, for AEs with a missing start date, the AE will be considered treatment-emergent unless there is additional information indicating that the AE started prior to study treatment and AEs for which the relationship is missing, will be considered related

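### SAP section 9 subtracts adverse event dates in the wrong order, and its unbounded partial-date rule would still give impossible durations once the order is corrected

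*SAP*

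**What the plan says.** SAP section 9 (Derived Data) is one short paragraph with three rules.

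- Duration: "Adverse event duration will be calculated as (Onset date – Resolution date) + 1".
- Partial dates: "if day is missing but month is available, the 15th of the month will be used as the date", and "If both month and day are missing, then January 15th of the year will be used".
- Capsule passage: "PillSense capsule passage will be calculated (Date of passage - Date of procedure"), that is, end minus start.

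No visible text requires an imputed resolution to fall on or after onset, or an imputed onset to fall on or before a known resolution. Nor does any tie an imputed date to capsule administration or study exit.

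Three other places in the SAP bear on the point. Section 4 limits follow-up: "Observation will take place for each Patient up to a maximum 21 days". Section 8.3 lists the event attributes to be tabulated as "AEs/SAEs characteristics including severity, relationship to procedure, relationship to device, action taken and outcome"; duration is not among them. Section 5.4 gives a default for treatment-emergent status: "For AEs with a missing start date, the AE will be considered treatment-emergent unless there is additional information". Section 6.5 repeats that default for the Safety Population.

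**The concern.** The subtraction runs start minus end. The added day shows that an inclusive day count was intended, and only resolution minus onset delivers one. The passage formula in the same paragraph runs the usual way, so this looks like a transposition.

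The natural repair is to swap the two dates and move on. That leaves the second fault in place. A fixed mid-month or mid-January substitute takes no account of the other date on the record or of the observation window. A corrected formula can therefore still return a negative duration, or one longer than the subject was observed. At stake is whether a variable that the SAP chose to define can be derived as specified without undocumented decisions by the programmer.

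**Working it through.** **Inputs.** The duration formula and the two partial-date rules are from SAP section 9. The 21-day observation limit is from SAP section 4. The example dates are mine and use the 2022 calendar. The plan gives no worked duration to reproduce.

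**1. Complete dates, order as written.** Let O be the onset date, R the resolution date and D the inclusive duration, so R − O = D − 1. The formula gives

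(O − R) + 1 = −(D − 1) + 1 = 2 − D.

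| True duration D | Result as written |
|---|---|
| 1 | 1 |
| 2 | 0 |
| 3 | −1 |
| 5 | −3 |
| 7 | −5 |
| 22 (day 0 to day 21) | −20 |

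The corrected order gives (R − O) + 1 = D in every row.

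**2. Partial dates, order corrected.**

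| Record | Imputed date | (R − O) + 1 | True |
|---|---|---|---|
| Onset 20 March; resolution 24 March, day missing | R = 15 March | (15 − 20) + 1 = −4 | 5 |
| Same event; resolution month and day missing | R = 15 January | −64 + 1 = −63 | 5 |
| Onset 2 March, day missing; resolution 5 March | O = 15 March | (5 − 15) + 1 = −9 | 4 |
| Capsule and onset 11 January; resolution 1 February, day missing | R = 15 February | 35 + 1 = 36 | 22 |

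In the last row observation ends on 1 February (day 21), so the imputed resolution falls 14 days after it.

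**3. Which bounds are needed.** I enumerated 365 capsule dates, all 253 onset and resolution pairs within days 0 to 21, and 9 patterns. In each pattern each date is full, lacks the day, or lacks month and day. That makes 365 × 253 × 9 = 831,105 cases, with study exit set at day 21.

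- *Order corrected, no bounds.* The minimum is −15 (onset known, resolution day missing), −349 (onset known, resolution month and day missing) and −13 (onset partial, resolution known).
- *Onset no earlier than the capsule, resolution no earlier than onset.* The −13 remains when onset is partial and resolution is known.
- *Also onset no later than a known resolution.* The minimum becomes 1 in all nine patterns, but the maximum is 36 against a possible 22. With onset known and the resolution day missing, 22,260 of 92,345 combinations (24%) are imputed after day 21.
- *Also both imputed dates no later than study exit.* Every duration lies between 1 and 22.

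These are counts of possible date combinations. They test the rule and say nothing about how often partial dates occur.

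**The case against.** The strongest reply is that this changes nothing that anyone will see. Duration is absent from the event summaries in SAP sections 5.4 and 8.3, and a programmer would spot the transposition at once. Subjects are observed for at most 21 days at one site, with event reviews within 7 days and, where the later contact takes place, between days 8 and 21. A date with an unknown month is hard to produce in that setting, yet the largest errors need one. Section 6.5 also has data that look erroneous investigated, and a negative duration would be an obvious trigger.

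Most of this stands and sets the size of the point. It does not remove it. A silent correction would be an undocumented departure from the SAP and would not supply the missing bounds. Investigating an odd value does not say what to impute instead. The redacted list of tables supports no inference either way.

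Two stronger readings are tempting and should not be drawn.

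- *Imputed onsets remove events from the treatment-emergent count.* With the capsule on 20 March and onset on 22 March with the day missing, the imputed onset is five days before the capsule. But sections 5.4 and 6.5 keep events with a missing start date as treatment-emergent by default, and the SAP nowhere directs that the imputed date set that status. No wrong count is shown.
- *The reversed order hides bad partial dates behind believable values.* As written, the first three partial-date records give +6, +65 and +11. The +65 is not believable under a 21-day limit, and the argument needs an apparent transposition to be programmed literally.

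**Conclusion.** Minor, and wrong as written. The reversed subtraction is certain from the text: it gives a wrong duration for every event with complete dates that lasts more than one day. The missing bounds are a separate fault that survives the obvious correction. They matter only for events with a partial onset or resolution date. The documents give no frequency for these; that they are rare is a judgement based on the short follow-up.

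The sensitivity and specificity tests, the predictive values and capsule transit do not use this derivation. No visible safety summary uses it either. A reader should not infer that the safety conclusions are at risk.

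**What to change.** Amend SAP section 9 as follows.

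1. Define duration as resolution minus onset, plus one day.
2. Impute a partial onset no earlier than the capsule date, unless the known date parts or other information show an earlier onset. Impute it no later than a known resolution date or study exit.
3. Impute a partial resolution no earlier than onset and, for events recorded as resolved during the study, no later than study exit.
4. Flag imputed durations in the listings.

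The cost is a few sentences of SAP text. No new data are needed and no analysis of an endpoint changes.

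The bounds make durations possible, not accurate. Onset on 20 March with the resolution day missing becomes 1 day when the truth is 5. Capsule and onset on 1 January with resolution on 2 January, day missing, becomes (15 − 1) + 1 = 15 days when the truth is 2. The flag in item 4 is there for that reason.

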### **10. DEVIATION FROM PROTOCOL**

The number and percentage of subjects with each type of protocol deviation will be presented. The number and percentage of a corrective action will be presented. A separate listing of protocol deviation type and onset date by subject will be presented.

## STATISTICAL ANALYSIS PLAN

[REDACTED]

[REDACTED]

[REDACTED]
